8. STUDY EVALUATIONS AND PROCEDURES

Study procedures will occur according the Time and Events Schedule.

Patients should be instructed to report adverse events associated with their in-home administration of the drug and any concerns that are identified between administration. Each report should be evaluated with respect to the need for an office visit for further assessment of safety.

Any adverse event identified by the patient during unscheduled visits should be recorded and followed, as appropriate, in accordance with Section 7.

8.1.1 Efficacy Measures

6-Minute Walk Test (6MWT)

The 6MWT should be performed at approximately the same time of day at each study visit and ideally, one of the first assessments to be performed.

An online tutorial on how to perform the 6MW test properly will be required of all clinical coordinators who will be performing the test. Only those who successfully complete the tutorial will be allowed to administer the test. In addition, a patient information booklet describing the appropriate effort and performance of the 6MW test will be given to each patient.

The 6MWT will be performed at the time points specified in the Time and Events Schedule using the methods described in the American Thoracic Society (ATS) Statement: Guidelines for the Six-Minute Walk Test ([50](#)). Testing should be performed in a location where a rapid,

appropriate response to an emergency is possible. The appropriate location of a crash cart should be determined by the physician supervising the facility. The test should be performed at approximately the same time of day when assessed and by the same evaluator whenever possible.

- Patient global assessment (based on the KCCQ instrument)
- Physician's Assessment of Functional Class
- Clinical Events: Death and hospitalizations

8.1.2 Safety Assessments

All safety evaluations will be performed at the time points listed in the Time and Events Schedule.

Any adverse events identified by the patient during unscheduled visits should be recorded and followed, as appropriate, in accordance with Section 7.

Patients should be instructed to report adverse events throughout their participation in the study. Each report should be evaluated with respect to the need for an office visit for further assessment of safety.

8.1.2.1 Medical and Medication History

To be completed at the final office visit in the parent study to ensure subjects meet the inclusion criteria for the study. Any clinically significant history should be noted in the eCRF.

8.1.2.2 Physical Examination (Including Height and Weight)

Abnormalities identified at the final office visit in the parent study will be documented in the subject's source documents and on the medical history eCRF. Changes after the Screening Visit will be captured as AEs on the AE eCRF page, as deemed by the Investigator.

8.1.2.3 Adverse Event Collection

Adverse events will be reported by the subject (or, when appropriate, by the subject's physician, a caregiver, surrogate, or the subject's legally acceptable representative) for the duration of the study. Non-serious adverse events will be followed by the investigator from the signing of the Informed Consent until the subject withdraws from the study, or the discontinuation of the study, whichever occurs first. Serious adverse events will be collected through in the same manner.

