1.3.1 Preclinical Information

Levosimendan's activity is mediated through unique mechanisms of action, including:

- Increased cardiac contractility by calcium sensitization of troponin C. (11-14)
- Vasodilation through the opening of potassium channels. (15-18)
- Cardioprotective effects via potassium channel opening in mitochondria. (19-22)

Levosimendan has an active metabolite that extends its effects well beyond the infusion period. Following intravenous or oral dosing, levosimendan is reduced by intestinal bacteria to form OR-1855 (limited activity) that is acetylated to form OR-1896, an active metabolite. While the parent half-life is approximately 1 hour and cleared a few hours after the end of intravenous infusion, OR-1896 has a prolonged half-life of 70-80 hours in heart failure subjects with roughly equal exposures of OR-1855 and OR-1896 maintained through deacetylation/ acetylation pathways. The OR-1896 metabolite has been shown to retain similar hemodynamic and pharmacologic properties of levosimendan and maintain roughly

equivalent effects to levosimendan in preclinical models. This activity occurs despite considerably lower plasma concentrations relative to levosimendan, an apparent result of a large percentage of unbound OR-1896 in circulation. (22-27). Thus, in extended repeated dosing, levosimendan is essentially an active prodrug to an active metabolite moiety, OR-1896.

Levosimendan has been shown to be a potent and selective phosphodiesterase-3 (PDE3) inhibitor *in vitro*. The drug is PDE3 selective with a PDE3/PDE4 inhibition ratio of 10,000. (15, 49). However, both isozymes must be inhibited in cardiomyocytes to exert an effect on the cAMP concentration and inotropic effects. The classical PDE inhibitors (i.e. milrinone, enoximone, and amrinone) inhibit both PDE3 and PDE4 at therapeutic concentrations (e.g. milrinone selectivity for PDE3 vs PDE4 is as low as 17-fold), which accounts fully for their inotropic effect.

OR-1896 is equipotent to levosimendan in its inotropic effects in whole cardiomyocytes and isolated contractile apparatus preparations. However, OR-1896 is profoundly less potent in the inhibition of both PDE3 and PDE4 isozymes. This supports the hypothesis that the main component of the inotropic effect for both levosimendan and OR-1896 is a result of their binding to troponin C and not through PDE inhibition. (49)

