2.3 Study Design

This extension study is designed to investigate the safety and efficacy of extended levosimendan in patients who previously received levosimendan in PH-HFpEF study sponsored by Tenax and may, in the investigator's opinion, derive benefit from continued treatment. Patients will be screened for eligibility at the last visit in the treatment period of the parent study. Eligible patients will be enrolled into the study immediately upon confirmation of eligibility so that levosimendan is not interrupted.

Efficacy assessments (6MWT, Patient global assessment (based on the KCCQ instrument), Physician's Assessment of Functional Class, Clinical Events; Death and hospitalizations) will be performed at 3, 6, 12, 24, 48, and yearly through Follow-up/Termination visit. For patients that transition from IV to oral (Week 0 and 6 or 8), the Time and Events Schedule for oral levosimendan should be followed. Patients will undergo a Follow-Up Visit (at termination) as soon as possible after study drug discontinuation, but within 2 weeks.

For patients that transition to oral levosimendan, the patient should be instructed to monitor their resting heart rate and blood pressure each day prior to the first dose. The patient should use the home monitoring device (provided at the initiation of the initial levosimendan study) to determine their resting heart rate and blood pressure after being seated at rest for at least 5 minutes. The heart rate and blood pressure readings should be recorded in the diary provided as well as the number of capsules the patient has taken each day. The patient should have their diary ready to review with the investigative site in each communication with the site and at office visits.

Patients whose BP falls below the specified range will be queried regarding any symptoms of hypotension which may result in the down titration of the levosimendan dose.

Patients whose heart rate exceeds the specified range will be queried regarding symptoms of worsening heart failure. An excessive heart rate in a patient with no evidence of worsening heart failure, suggests that the increased heart rate is a direct drug effect requiring adown titration of the levosimendan dose.

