7.1.4 IV-Oral Transition Week 6 – Final Visit

During this visit, the following procedures will be performed:

- Vital signs and ECG
- Physical Exam
- Hematology and chemistry blood samples
- Assess adverse events
- Pharmacokinetic sample
- 6MWT
- NYHA Functional Class
- Kansas City Cardiomyopathy Questionnaire (KCCQ)

Once a patient transitions to oral levosimendan, all references in this protocol to the administration of IV levosimendan, will no longer apply for that patient. All study drug and ancillary supplies related to the administration of IV levosimendan will be returned to the central pharmacy for destruction.

7.1.5 IV-Oral Transition Week 8

This visit is only required for patients who titrated (up or down) at the Week 6 visit.

During this visit, the following procedures will be performed:

- Vital signs
- Physical Exam
- Hematology and chemistry blood samples
- Assess adverse events
- Pharmacokinetic sample
- 6MWT
- NYHA Functional Class
- Kansas City Cardiomyopathy Questionnaire (KCCQ)

The Physical Exam, 6MWT, NYHA Functional Class, and KCCQ do not need to be performed for patients who are scheduled for a Week 8 visit, due to either up or down titration of study drug.

Following the Final Evaluation (either Week 6 or Week 8), patients will continue to visit the investigational site at weeks 3, 6, 12, 24, 48, and yearly through the Follow-Up Visit (at termination) and/or Termination visit. These visit windows will be based on the date the patient originally enrolled in the TNX-LVO-05 study. Visits that overlap may be combined into one visit.

Patients unable to return at the scheduled Week 6 or 8 visit, may have their final visit extended.

7.2 Weeks 3, 6, 12, 24, 48, and yearly through the Follow-up and/or Termination

visit (Office Visits)

Visits at Weeks 3, 6, 12, 24, 48, and yearly through the Follow-up and/or Termination visit should be performed within ± 72 hours of the scheduled weekly visit. These visits may be performed at the investigator's office. For any patients who remain on IV levosimendan, the Follow-Up Visit (at termination) will be calculated as the earlier of two years from the subject's date of entry into the TNX-LVO-05 Study or as soon as possible after study discontinuation, but within 1 week.

During this visit, the following procedures will be performed:

- Vital signs
- Physical Exam
- Hematology and chemistry blood samples
- Body Weight
- 6MWT
- Kansas City Cardiomyopathy Questionnaire (KCCQ)

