9. ADVERSE AND SERIOUS ADVERSE EVENTS ASSESSMENT

9.1 Definition of Adverse Events, Period of Observation, Recording of Adverse Events

An Adverse Event (AE) is any untoward medical occurrence in a clinical investigation subject administered a pharmaceutical product and that does not necessarily have a causal relationship with this treatment. An AE can therefore be any unfavorable and unintended sign (including an abnormal laboratory finding), symptom, or disease temporally associated with the use of a medicinal (investigational) product, whether or not related to the medicinal (investigational) product (ICH Guidance E2A 1994).

All AEs are collected from the time the informed consent is signed until the subject discontinues and are to be recorded on the appropriate AE pages in the eCRF and in source documents. Where possible, a diagnosis, rather than a list of symptoms, should be recorded. If a diagnosis has not been made, then each symptom should be listed individually. In addition to untoward AEs, unexpected benefits outside the investigational product indication should also be captured on the AE eCRF.

All AEs must be followed to closure (the subject's health has returned to his/her baseline status or all variables have returned to normal), an outcome is reached, stabilization (the Investigator

does not expect any further improvement or worsening of the event), or the event is otherwise explained regardless of whether the subject is still participating in the study. When appropriate, medical tests and examinations are performed so that resolution of event(s) can be documented.

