9.2.4 Serious Adverse Event Collection Timeframe

SAEs must be recorded from the time of signature of Patient Informed Consent through 30 days after completion of the last dose. The onset date of the SAE is defined as the date the event meets serious criteria. The resolution date is the date the event no longer meets serious criteria, the date the symptoms resolve, or the event is considered chronic. In the case of

hospitalizations, the hospital admission and discharge dates are considered the onset and resolution dates, respectively.

In addition, any signs or symptoms experienced by the subject prior to study entry or leading up to the onset date of the SAE or following the resolution date of the SAE, must be recorded as an AE, if appropriate.

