2.2 Study Design

2.2.1 Overview

This extension study is designed to investigate the safety and efficacy of extended levosimendan in patients who previously received levosimendan in the Pulmonary Hypertension with Heart Failure and Preserved Left Ventricular Ejection Fraction (PH-HFpEF) study sponsored by Tenax and may, in the investigator's opinion, derive benefit from continued treatment. Patients will be screened for eligibility at the last visit in the treatment period of the parent study. Eligible patients will be enrolled into the study immediately upon confirmation of eligibility so that levosimendan is not interrupted.

Efficacy assessments (Six-minute walk test (6MWT), Patient global assessment (based on the Kansas City Cardiomyopathy Questionnaire (KCCQ) instrument), Physician's Assessment of Functional Class (measured by New York Heart Association (NYHA) functional class assessment), Clinical Events (death and hospitalizations)) will be performed at 3, 6, 12, 24, 48 weeks and yearly through the Follow-up/Termination visit. Patients will undergo a follow-up visit (at termination) as soon as possible after study drug discontinuation, but within one (1) week.

Patients whose blood pressure (BP) falls below the specified range will be queried regarding any symptoms of hypotension which may result in the down titration of the levosimendan dose. Patients whose heart rate exceeds the specified range will be queried regarding symptoms of worsening heart failure. An excessive heart rate in a patient with no evidence of worsening heart failure, suggests that the increased heart rate is a direct drug effect requiring a down titration of the levosimendan dose.

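### Protocol Sections 8.1.2.3 and 9.1 end SAE collection at study exit, while 9.2.4 runs it to 30 days after the last dose; new SAEs in between are kept or lost according to the section a site follows

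*Protocol*

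**What the plan says.** Three protocol sections set an end to collection.

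- **Section 8.1.2.3** follows non-serious events from consent "until the subject withdraws from the study, or the discontinuation of the study, whichever occurs first". Its next sentence deals with serious events: "Serious adverse events will be collected through in the same manner".
- **Section 9.1** says: "All AEs are collected from the time the informed consent is signed until the subject discontinues". It makes no exception for SAEs, and does not say whether it means discontinuing drug or study.
- **Section 9.2.4**, the section on the SAE timeframe, says: "SAEs must be recorded from the time of signature of Patient Informed Consent through 30 days after completion of the last dose".

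The last scheduled contact is the Follow-Up Visit, at which the Time and Events Schedule marks adverse events and SAEs. Protocol Section 2.3 places it "as soon as possible after study drug discontinuation, but within 2 weeks". Sections 6.2 and 7.2 place it, for patients on IV drug, "as soon as possible after study discontinuation, but within 1 week". SAP 2.2.1 has "as soon as possible after study drug discontinuation, but within one (1) week". No contact is scheduled at day 30.

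SAP 3.5.1 defines a treatment-emergent event by its start date relative to first dose and sets no upper limit after the last dose.

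**The concern.** Two sections close the SAE window when the patient leaves the study. A third keeps it open to a fixed point after the last dose. A site that works from 8.1.2.3 or 9.1 has no instruction to look for a new SAE after exit, whereas a site that works from 9.2.4 must record it.

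Adverse event incidence is the primary endpoint, and death and hospitalization are a secondary one. The SAP's list of outputs has no separate table or listing for deaths or hospitalizations, so as far as that list shows they reach the report through the adverse event records. With no end to the treatment-emergent window, a day-20 death counts if the site recorded it and is absent if it did not. In a cohort this small, one such event is visible in the result, and an event never collected may not be recoverable at database lock.

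**Working it through.** The plan states no figure to reproduce. The check compares the windows and then sizes the gap.

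**1. The clocks.** Section 8.1.2.3 runs to study exit. I read 9.1 the same way, since the Schedule still collects events at the Follow-Up Visit. Section 9.2.4 runs from the last dose. An SAE after stopping drug but before study exit is therefore collected under all three. The disputed interval is from study exit to day 30.

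**2. Length of the interval.** Uncovered days = 30 − day of study exit after the last dose. For the IV rule I assume that drug and study are stopped together.

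| Exit | Uncovered days |
|---|---|
| Follow-Up Visit on day 14 (Protocol 2.3) | 30 − 14 = 16 |
| Follow-Up Visit on day 7 (Protocol 6.2 and 7.2, SAP 2.2.1) | 30 − 7 = 23 |
| Day of last dose, no visit | 30 − 0 = 30 |

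**3. Active metabolite at exit.** Protocol Section 1.3.1 states: "OR-1896 has a prolonged half-life of 70-80 hours in heart failure subjects". Fraction remaining = 0.5^(hours ÷ half-life).

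- Day 7 (168 h): 0.5^(168/70) = 19% to 0.5^(168/80) = 23%.
- Day 14 (336 h): 0.5^(336/70) = 3.6% to 0.5^(336/80) = 5.4%.

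Some active metabolite is therefore still present when a patient exits at either visit.

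**4. Illustrative size for deaths.** Risk over d days = 1 − exp(−λd), with constant hazard assumed. Two rates come from the protocol's background text:

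- Section 1.2 gives 5-year survival below 50%. Taken as 50%, λ = ln 2 ÷ (5 × 365.25) = 0.00038 per day.
- Section 1.3.4 gives 15 + 8 + 6 = 29 deaths among 307 patients in the oral study in severe heart failure. Over an assumed 180 days, λ = −ln(1 − 29/307) ÷ 180 = 0.00055 per day.

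The protocol gives no sample size for this study. I take n = 37, the number randomized in the parent study (Section 1.3.5), as the most that could enter. Expected deaths = 37 × risk, and the chance of at least one = 1 − (1 − risk)^37.

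| Uncovered days | Risk, 50% at 5 years | Expected; chance of ≥1 | Risk, 29/307 in 180 days | Expected; chance of ≥1 |
|---|---|---|---|---|
| 16 | 0.61% | 0.22; 20% | 0.88% | 0.32; 28% |
| 23 | 0.87% | 0.32; 28% | 1.26% | 0.47; 37% |
| 30 | 1.13% | 0.42; 34% | 1.64% | 0.61; 46% |

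One death among 37 is 1/37 = 2.7 percentage points, and more if fewer enter.

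**The case against.** The best defence is that 9.2.4 is the specific rule: it is the section on the SAE timeframe and it is mandatory in tone. The sentence in 8.1.2.3 is visibly garbled, and the manner it refers to could be the method of reporting rather than the period. Appendix 1 also records that the 30-day sentence was added in Version 3.0 to give the full recording period, which shows the sponsor's intent. This makes 9.2.4 the likelier choice for a careful site. It does not remove the conflict: the sentence just before the garbled one defines a period, 9.1 gives the short period independently, and nothing ranks the sections.

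The defence is right on scope, and several stronger readings fail.

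- **That nothing is collected while metabolite persists.** Five half-lives are 5 × 70 h = 350 h to 5 × 80 h = 400 h, or 14.6 to 16.7 days. A reader might take all of that as unobserved. It is not, because 8.1.2.3 runs to study exit rather than last dose. Section 3.4 asks for the Follow-Up Visit whenever possible after stopping drug, and the Schedule collects events there.
- **That patients who stop for an adverse event are lost if they then die of it.** Section 9.1 follows reported events to closure whether or not the patient is still in the study, and 9.2.2 follows SAEs until they settle or the patient dies. Only new events are exposed.
- **That risk after stopping is several times the background rate.** Attachment 3 and Section 5.4.1 do make some safety stops study exits, so the gap can fall on such patients. But no figure in the documents gives a higher rate after stopping.
- **That the SAP should cut SAEs off at last recorded dose plus 30 days.** SAP 3.3.5 imputes the last oral dose to as much as 365 days after the recorded one, or to 1 February 2023. Such a cut-off could discard SAEs that occurred on treatment.

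**Conclusion.** The contradiction stands in the Version 4.1 text and should be corrected. It affects new SAEs between study exit and day 30: 16 to 23 days when the patient exits at a Follow-Up Visit held at its latest permitted day, and up to 30 days only with exit on the day of the last dose and no visit.

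The death figures (0.2 to 0.6 expected, 20-46% chance of at least one) show scale and are not forecasts. They assume a constant hazard, rates from other populations, entry of all 37 patients, and a gap that goes wholly uncovered for each of them. Fewer entrants, or sites that follow 9.2.4, would lower them. The analysis is descriptive, so no test is affected; the harm is to the completeness and comparability of the safety counts.

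SAP Section 4 cites protocol v5.0, which is not among the documents. Whether that version settles the conflict cannot be told from them.

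**What to change.** 1. Amend 8.1.2.3 and 9.1 to agree with 9.2.4: SAEs, including deaths and hospitalizations, are collected through 30 days after the last dose, regardless of withdrawal from treatment or study, unless the patient withdraws consent to contact.
2. State in the same two sections that non-serious events are collected through the Follow-Up Visit, as the Schedule already marks, and reconcile the one-week and two-week timings of that visit.
3. Add a day-30 telephone contact to the Schedule.
4. Leave the treatment-emergent definition in SAP 3.5.1 without a cut-off tied to the last recorded dose date.

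The cost is a few sentences of protocol text and one call per patient, which 9.2.4 already implies. For patients who have already left, sites can be asked whether any SAE occurred within the 30 days, where consent allows.

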8.1.2.4 Vital Signs

Blood pressure should be determined by cuff (using the same method, the same arm, and in the same position throughout the study, as appropriate). Any clinically significant deviations from baseline vital signs which are deemed clinically significant in the opinion of the Investigator are recorded as an AE.

Vital signs and body weight should be recorded according to the [Time and Events Schedule](#) and include: body temperature, heart rate, respiratory rate, and blood pressure [systolic and diastolic blood pressure].

8.1.2.5 Clinical Laboratory Evaluations

All blood laboratory test collections must be performed **prior to** study drug dosing (where other exclusions do not apply). Blood specimens for hematology and serum chemistry will be collected, and results obtained by local laboratories.

All clinical laboratory assays will be performed according to the laboratory's normal procedures. Reference ranges are supplied by the laboratory and used to assess the clinical laboratory data for clinical significance and out-of-range pathological changes. The Investigator should assess out-of-range clinical laboratory values for clinical significance, indicating if the value(s) is/are not clinically significant (NCS) or clinically significant (CS). Abnormal clinical laboratory values, which are unexpected or not explained by the subject's clinical condition may be, at the discretion of the Investigator or Sponsor, repeated until confirmed, explained, or resolved as soon as possible.

Blood samples for hematology and serum chemistry will be taken at the time points detailed in the Time and Events Schedule. The investigator must review the laboratory report, document this review, and record any clinically relevant changes occurring during the study in the adverse event section of the eCRF. The following tests may be performed by the local laboratories and results entered into the eCRF, as shown in the [Time and Events Schedule](#):

Hematology and Coagulation Panel

Hematocrit
Hemoglobin
White blood cell (WBC) count with differential
Platelet count
Prothrombin time
Partial thromboplastin time

Serum Chemistry Panel

Sodium
Potassium
Bicarbonate
Blood urea nitrogen (BUN)
Creatinine
NT-proBNP

Child-Pugh Class is only required for patients who have documented liver disease.

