Body Weight	X	X					X	X
Serum Chemistry and Hematology (Local Lab) ⁷	X	X			X ⁶	X	X	X
Child Pugh Class ⁷	X							X
Vital Signs	X	X	X	X	X	X	X	X
Pharmacokinetic Sample		X ²		X	X ²	X ²		
Electrocardiogram (ECG)	X	X			X ⁶	X		X
Levosimendan Administration (oral) / Dose Titration ³		X	X	X	X ⁴			
NYHA Functional Class	X	X			X ⁶	X	X	X
6 - Minute Walk Test	X	X			X ⁶	X	X	X
Adverse Events/SAEs ⁸	X	X	X	X	X	X	X	X
Concomitant procedures and medications	X	X	X	X	X	X	X	X
KCCQ Assessment ⁹	X	X			X ⁶	X	X	X

Footnotes for Time and Events Schedule

1. Visits will be scheduled 7-9 days following completion of the levosimendan IV dose and every 14 days through the oral levosimendan transition (+/- 48 hrs); at the Investigator's discretion, Week 2 and 4 visits may be performed remotely.
2. Blood sample to be taken prior to the patient's daily dose of oral levosimendan.
3. The first dose of oral levosimendan to be taken 7-9 days after the patient's final weekly IV levosimendan dose. Once oral levosimendan begins, subjects must completely discontinue weekly levosimendan infusions. Patients will begin a daily dose regimen of 1mg daily and titrated at 1mg increments every 2 weeks, as tolerated.
4. At the investigator's discretion, patients that have not demonstrated an adequate response to drug therapy and a tolerance to the 1mg levosimendan TID may be titrated to 1mg QID. Patients that have not tolerated 1 mg levosimendan TID should be down titrated to 1mg BID. All patients that are titrated at Week 6 should return for a Week 8 visit.
5. Due to the COVID-19 pandemic, the investigator may have a phone conversation with the patient rather than having the patient come in for an office visit. The phone conversation should include the following, as reported by the patient; adverse events, concomitant medications (new or changed), concomitant procedures, and blood pressure & heart rate (use provided home blood pressure cuff).
6. If a patient is up or down titrated and therefore scheduled for a Week 8 visit, these procedures do not need to be performed at Week 6.
7. Local labs will be drawn (including NT-proBNP). Child-Pugh Class is only required for patients with documented liver disease.
8. During routine visits and throughout a participation in the study, patients should be queried for any new or changes to AEs, concomitant medications, concomitant procedures, hospitalizations, and/or emergency room visits

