3.2 Exclusion Criteria

Subjects are excluded from the study if any of the following exclusion criteria are met.

1. Discontinued treatment in the parent study for any reason other than study completion or Sponsor termination of the study.
2. Pregnant or breastfeeding women.
3. Local access to commercially available levosimendan.
4. Inability to comply with planned study procedures
5. Patients with scheduled lung or heart transplant or cardiac surgery
6. Dialysis developed since enrollment in parent study (either hemodialysis, peritoneal dialysis, continuous venovenous hemofiltration, or ultrafiltration)

7. Estimated glomerular filtration rate (eGFR) < 30 mL/min/1.73m²
8. Liver dysfunction with Child Pugh Class B or C (see [Attachment 1](#))
9. Evidence of systemic bacterial, systemic fungal, or viral infection refractory to treatment
10. Weight > 150 kg
11. Systolic blood pressure (SBP) cannot be managed to ensure $SBP \geq 100$ mmHg at initiation of study drug
12. Heart rate ≥ 100 bpm with study drug, persistent for at least 10 minutes at screening.
13. Hemoglobin < 80 g/L
14. Serum potassium < 3.0 mmol/L or > 5.5 mmol/L at baseline that is unresponsive to management

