14. ATTACHMENTS

14.1 ATTACHMENT 1: Child Pugh Classification

Scoring System

The score employs five clinical measures of liver disease.¹ Each measure is scored 1-3, with 3 indicating most severe derangement.

Measure	1 point	2 points	3 points
Total bilirubin μmol/l (mg/dl)	<34 (≤2)	34-50 (2-3)	>50 (>3)
Serum albumin, g/l	>35	28-35	<28
PT INR	<1.7	1.71-2.30	> 2.30
Ascites	None	Mild	Moderate to Severe
Hepatic encephalopathy	None	Grade I-II (or suppressed medication)	Grade III-IV (or refractory)

Different textbooks and publications use different measures. Some older reference works substitute PT prolongation for INR.

In primary sclerosing cholangitis (PSC) and primary biliary cirrhosis (PBC), the bilirubin references are changed to reflect the fact that these diseases feature high conjugated bilirubin levels. The upper limit for 1 point is 68 μmol/l (4 mg/dl) and the upper limit for 2 points is 170 μmol/l (10 mg/dl).

Classification designation

Chronic liver disease is classified into Child Pugh class A to C, employing the added score from above.

Points	Class
5-6	A
7-9	B
10-15	C

Reference

1. Pugh RN et al. Transection of the oesophagus for bleeding oesophageal varices. Br J Surg. 1973; 60(8):646-9.

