3.4.1 Primary Endpoints

The primary endpoints (Safety measures) are as follows:

- Incidence and severity of treatment-emergent adverse events (TEAEs),
- Incidence and severity of abnormal clinical laboratory test results (hematology, chemistry),
- Incidence of abnormal physical examination results,
- Incidence of abnormal vital sign values (blood pressure [BP] and pulse rate [PR]), and
- Incidence of abnormal 12-lead electrocardiogram (ECG) results or values.

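### The protocol's laboratory panel omits bilirubin and albumin and does not name INR, so Child-Pugh Class A cannot be confirmed from it, and the chemistry part of the primary safety endpoint has no liver analyte

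*Protocol*

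**What the plan says.** Exclusion 8 (Protocol 3.2 and the synopsis) removes patients with "Liver dysfunction with Child Pugh Class B or C". The Time and Events Schedule has a separate row for the class, marked at the final parent-study visit and at the termination visit. Footnote 7 limits it: "Child-Pugh Class is only required for patients with documented liver disease". Section 8.1.2.5 repeats that limit.

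Attachment 1 gives the scoring: "The score employs five clinical measures of liver disease". They are total bilirubin, "Serum albumin, g/l", INR, ascites and encephalopathy. Each scores 1 to 3, and the sum gives Class A (5-6), B (7-9) or C (10-15).

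The only laboratory list is in 8.1.2.5, introduced with "The following tests may be performed by the local laboratories and results entered into the eCRF":

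- Hematology and coagulation: hematocrit, hemoglobin, white cells with differential, platelets, prothrombin time, partial thromboplastin time.
- Chemistry: sodium, potassium, bicarbonate, BUN, creatinine, NT-proBNP.

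The primary endpoint includes chemistry results (Protocol synopsis; SAP 2.3.1 and 3.4.1). SAP 3.5.2 calculates changes from baseline, flags abnormal values and lists the clinically significant ones.

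**The concern.** The protocol uses a score in an eligibility criterion and schedules it again at the end of the study, yet the only list of tests it gives lacks two of the score's inputs and does not name a third. For a patient with documented liver disease, a site that drew only the listed tests could not show that the patient is in Class A, which is what clearing exclusion 8 requires.

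The second consequence reaches every patient. Chemistry is part of the primary safety endpoint, and no listed chemistry analyte reflects the liver. Oral treatment is planned for 3 years after transition at up to 4 mg a day. PERSIST, the chronic oral study that the protocol describes, used up to 1 mg twice daily for at least 180 days. If nothing hepatic is measured, a laboratory listing with no liver abnormality shows only that the tests were not done.

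**Working it through.** There is no plan figure to reproduce: the study has no hypothesis test and no calculated sample size. The check matches two lists and then bounds the score.

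**Step 1. Match the Attachment 1 items to the protocol's sources.**

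| Item | Source in the protocol |
|---|---|
| Total bilirubin | not in 8.1.2.5 |
| Serum albumin | not in 8.1.2.5 |
| INR | prothrombin time listed, INR not named |
| Ascites | clinical examination |
| Encephalopathy | clinical examination |

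**Step 2. Bound the score, taking INR as known.** Let K = INR + ascites + encephalopathy points (3 to 9). Let b and a be the bilirubin and albumin points, each 1 to 3. Then total = K + b + a, which runs from K + 2 to K + 6.

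| K | Combinations giving K | Range of total | Possible class |
|---|---|---|---|
| 3 | 1 | 5-9 | A or B |
| 4 | 3 | 6-10 | A, B or C |
| 5 | 6 | 7-11 | B or C |
| 6 | 7 | 8-12 | B or C |
| 7 | 6 | 9-13 | B or C |
| 8 | 3 | 10-14 | C |
| 9 | 1 | 11-15 | C |

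**Step 3. Read off the eligibility decision.**

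- Class A is confirmed only if K + 6 ≤ 6, that is K ≤ 0. Since K is at least 3, this never happens.
- Class B or C is established if K + 2 ≥ 7, that is K ≥ 5. This covers 6 + 7 + 6 + 3 + 1 = 23 of 27 combinations.
- A versus B/C stays open for K = 3 or 4, which is 1 + 3 = 4 of 27 combinations.
- The exact class is fixed only for K = 8 or 9, which is 3 + 1 = 4 of 27, all Class C.

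These are counts of score patterns, not proportions of patients. The patterns are not equally likely, and the open ones (K = 3 or 4) are those with at most one mild derangement among the three items.

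**Step 4. If INR is not reported either.** Let E = ascites + encephalopathy points (2 to 6). With three items unknown, the total runs from E + 3 to E + 9. Class A would need E + 9 ≤ 6, which is impossible. B or C is established if E + 3 ≥ 7, that is E ≥ 4. A versus B/C is open for E = 2 or 3.

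**Step 5. Count liver analytes in the chemistry panel.** None of sodium, potassium, bicarbonate, BUN, creatinine or NT-proBNP is one: 0 of 6. Prothrombin time partly reflects liver function, but it sits in the coagulation panel.

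**The case against.** **The list is permissive, and the class has its own row.** The tests in 8.1.2.5 may be done; the list neither requires them nor excludes others. A site that must score a patient can read Attachment 1 and order what it needs. This stands against any claim that the values were never obtained. What remains is that the protocol names no source and no eCRF entry for them.

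**Entry eligibility may rest on other results.** It is confirmed at the final parent-study visit. The parent protocol, its laboratory panel and the eCRF are not available here, so bilirubin and albumin may have been on hand from parent-study or standard-of-care tests. This stands for entry. It does not supply the termination score.

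**Few patients are affected.** Only patients with documented liver disease are scored, and no document says how many there are. This stands for Child-Pugh, but the missing liver chemistry concerns all patients.

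**Hepatic events are still captured.** Protocol 9.1 and 9.1.6 collect adverse events, including relevant abnormal laboratory findings, throughout. A reader might infer that the study could not detect a liver problem at all. The documents do not support that; what is absent is routine liver chemistry.

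**ALT and AST are not needed for Child-Pugh.** Correct. The protocol's safety background names hypotension and tachycardia as the main concerns, and its most frequent oral adverse events include nothing hepatic. The case for the enzymes rests only on the primary chemistry endpoint and can be judged separately.

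**Conclusion.** The point holds in a limited form. Followed as written, the panel can establish exclusion 8 (three-item subtotal of 5 or more) but can never clear a patient of it, and it leaves the decision open at subtotals of 3 or 4. It also gives the chemistry part of a primary safety endpoint no hepatic content (0 of 6). Apart from prothrombin time, liver effects during up to 3 years of oral treatment would surface through reported adverse events rather than routine laboratory data.

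Two stronger readings go too far. One is that exclusion 8 cannot be applied at all: the arithmetic shows that it can be met without the missing values, and other sources may have existed at entry. The other is that missing items would be scored as normal, moving patients into Class A: no text says how a missing item is scored.

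The conclusion assumes that ascites and encephalopathy are known from examination and, in the main calculation, that INR is available with the prothrombin time. It rests on protocol version 4.1. SAP section 4 refers to version 5.0, which could not be checked. This is a worthwhile, inexpensive improvement and does not undermine the study.

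**What to change.** In 8.1.2.5, add total bilirubin, albumin, ALT and AST to the chemistry panel, and report INR with the prothrombin time. Draw them at visits where chemistry is already scheduled, including transition Week 0 and termination, and provide eCRF fields. With ascites and encephalopathy from examination, the termination score is then fully determined. The new values enter the SAP 3.5.2 outputs, mainly as listings of clinically significant results.

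This cannot repair exclusion 8 for patients already enrolled, because eligibility is not reconfirmed at transition. For those with documented liver disease, state where the entry bilirubin and albumin came from. If data collection is complete, the CSR should state that hepatic chemistry was not part of the protocol panel, so that an absence of liver findings in the laboratory listings is not read as evidence of hepatic safety.

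The cost is a few analytes on existing local draws, the eCRF fields, and some incidental abnormal values to review. No visit, procedure or staff is added.
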